#### 3.2 Clinical Trial Sample Screening

#### 3.2.1 Sample Type and Size

The samples in this study are confirmed tissue biopsy samples, which are retrospective samples.

The total number of samples in this clinical trials is 1052. It is planned to be carried out in at least 4 clinical trial institutions, and 3 of them will enroll no less than 255 samples. In case of objective reasons, when the sample size is insufficient, the centers can make appropriate adjustments or increase clinical trial institutions under the premise of ensuring the total amount. It is planned that the ratio of positive samples shall not be less than 30%, and the rare mutation types shall be counted according to the clinical occurrence, which should be statistically significant. Gene locus below the above standards can no longer be included in clinical data statistics.

The analysis of the selected number of case samples is statistically significant, and the conclusions obtained are reasonable and effective, which can make a scientific evaluation of the Genetron Lung Cancer Panel and save social costs to the greatest extent. If all types of specimens are not received as planned due to other reasons, the final type and quantity of specimens shall be subject to the actual collected specimens after negotiation and agreement between the two parties.

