Wherein, in the treatment of non-small cell lung cancer, the main molecular targeted therapy is epidermal growth factor receptor (EGFR). The efficacy of molecularly targeted drugs is significantly different between different lung cancer patients of the same tissue type and different lung cancer pathological tissue types. The EGFR mutation rate in Asian patients with advanced lung adenocarcinoma is as high as 50%, and there are many EGFR tyrosine kinase inhibitor (TKI) is listed in China and used for clinical treatment. In addition to EGFR, anaplastic lymphoma kinase (ALK) fusion gene and ROS1 fusion gene are also divided into subgroups of NSCLC molecules with specific clinical and pathological characteristics, thereby providing new molecular targets for the treatment of lung cancer. In addition, biomarkers related to lung cancer include HER2, KRAS, BRAF V600E gene mutations, and MET exon 14 skipping mutations. At present, the molecular classification of lung cancer plays an important role in guiding clinical treatment plans, drug selection, and establishing an individualized treatment model for molecular classification. Patients with specific genotypes can only benefit from the corresponding targeted drugs. Therefore, effective and accurate detection of tumor gene status and accurate molecular

subtype differentiation of NSCLC patient populations have become an important basis for patient treatment, prognosis evaluation, and efficacy monitoring.

At present, the routine detection methods for clinical gene detection are fluorescent quantitative PCR, nucleic acid sequence determination, FISH and so on. However, to carry out the above-mentioned gene detection at the same time requires the combination of multiple technology platforms and multiple methods. The large sample size requirements, the complex operation process, and the long detection cycle pose very high challenges to personnel, technology, equipment, etc., which is a serious departure from the clinical goal of quickly and accurately obtaining patient clinical medication information.

The Genetron Lung Cancer Panel is developed by Genetron Health (Beijing) Co., Ltd.. It is used to detect EGFR, KRAS, BRAF, HER2, PIK3CA, ALK, ROS1, MET gene mutations or fusions in non-small cell lung cancer patients. The Genetron Lung Cancer Panel is prepared in a clean production workshop that meets the requirements of the "In Vitro Diagnostic Reagent Production Implementation Rules", and has passed the self-test.

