## 2 Research Purpose

The main purpose of this study is: by evaluating the Genetron Lung Cancer Panel to compare the results of simultaneous detection with similar products on the market and the Sanger sequencing method, and to calculate the coincidence rate and consistency of the assessment reagents and the comparison method. The safety and effectiveness of the product are confirmed and evaluated. Meanwhile, the accuracy of the Genetron Lung Cancer Panel for the following drug companion diagnostic tests: EGFR gene 19 exon deletion and L858R point mutation in gefitinib tablets, erlotinib hydrochloride and icotinib hydrochloride tablets, T790M point mutation in methanesulfonate acid osimertinib tablets, ALK gene fusion and ROS1 gene fusion in crizotinib capsules.

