#### 3.2.2 Inclusion Criteria, Exclusion Criteria Rejection Criteria of Study Subjects

#### 3.2.2.1 Inclusion Criteria

- (1) Clinically diagnosed as non-small cell lung cancer samples (mainly lung adenocarcinoma and some lung squamous cell carcinoma, adenosquamous carcinoma, large cell carcinoma, etc.), and a small number of other cancer types are enrolled as interference samples.
- (2) Collect some samples of relevant medical information before and after the use of targeted drugs.

  This part of the samples should have relevant previous molecular diagnosis results.

- (3) Able to provide samples in time according to the requirements of the plan: samples for DNA/RNA extraction: 10 pieces of 10 µm thickness for each sample or 10 pieces of paraffin rolls. Samples for FISH experiment: 5 slices of 3-4µm thickness.
- (4) The pathological examination conforms to the types of tissue samples listed in the above table. The HE staining results show that the tumor content is not less than 50%, and the paraffin slice damage should be avoided.
- (5) The sample should have corresponding basic clinical information, including: patient visiting number/medical record number/specimen number, age, gender, pathological diagnosis result, molecular diagnosis result (if any).

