#### 3.2.4 Sample Code

In principle, one subject only provides one sample, and each subject should have a unique clinical trial number (secondary code). After the samples are entered into the group and before the experiment operation, the blind-editing staff will mark the secondary code outside the sample tube, and carefully record the primary code (patient visit number/medical record number/specimen number) and the correspondence table of the secondary code as the blind bottom save. The blind-editing file is kept independently by the blind-editing staff until the blind is solved. Under no circumstances should the blindness be solved during the tail.

During the experiment operation, only the secondary code of the sample is reflected.

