#### 3.3.2 Comparison Method

The specific sites and corresponding kits are shown in the following table

Table 1. Selection of comparison methods for each gene

Gene	Comparison method		
EGFR	cobas EGFR Mutation Test V2		
ALK	Vysis ALK Break Apart FISH Probe Kit		
ROS1	Vysis 6q22 ROS1 Break Apart FISH Probe		
ROS1*	ROS1 gene fusion detection kit (fluorescence PCR method)		
KRAS	KRAS gene mutation detection kit (fluorescence PCR method)		

PIK3CA	PIK3CA gene mutation detection kit (fluorescence PCR method)
BRAF	BRAF gene mutation detection kit (fluorescence PCR method)
MET	/
HER2	/

\* On the basis of choosing the Vysis 6q22 ROS1 Break Apart FISH Probe kit as a comparison method for the ROS1 gene, add no less than 200 samples for ROS1 gene fusion detection kit (fluorescent PCR method) to perform the comparative study of companion diagnostic reagents.

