### 4 Statistical Analysis

#### 4.1 The coincidence rate of the panel and the comparison method

For each gene locus, a four-grid table was used to calculate the positive coincidence rate, negative coincidence rate, positive predictive value, negative predictive value, total coincidence rate and 95% confidence interval of the assessment reagent and the comparison method. Using statistical software, Kappa test is used to determine whether the two detection methods are statistically significant.

Table 2. Results statistics

Genetron Lung Cancer	Comparison method		Total
Panel	Positive	Negative	
Positive	A	В	A+B
Negative	C	D	C+D
Total	A+C	B+D	A+B+C+D

A sample with a mutation genotype is judged as positive, and a sample with no mutation genotype is judged as negative

The calculation formula is:

Positive coincidence rate=A/(A+C)×100%

Negative coincidence rate =  $D/(B+D) \times 100\%$ 

Positive predictive value (PPV)=A/(A+B)×100%

Negative predictive value (NPV)=D/(C+D)×100%

Total coincidence rate=(A+D)/(A+B+C+D)×100%

95% confidence interval calculation formula:  $p\pm1.96\times[p(1-p)/n]^{1/2}$  (where p is the positive coincidence rate, negative coincidence rate, positive predictive value, negative predictive value, total coincidence rate, n is the sample size, if p>0.9, use Wilson score method for correction).

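### Section 3.2.1 lets gene loci be left out of the statistics against standards that have no unit or threshold, and the companion-diagnostic loci are not exempt

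*Combined protocol and SAP*

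**What the plan says.** Section 3.2.1 (Sample Type and Size) plans 1,052 samples and then sets two standards in one sentence, which begins "It is planned that the ratio of positive samples shall not be less than 30%, and the rare mutation types shall be counted" and goes on to ask that the counting follow clinical occurrence and be statistically significant. The next sentence is the rule at issue: "Gene locus below the above standards can no longer be included in clinical data statistics". The same section lets the final type and quantity of specimens follow what was actually collected, by agreement between the parties.

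Three other places bear on it:

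- Section 2 (Research Purpose) makes accuracy for companion-diagnostic use a purpose of the study. It names EGFR exon 19 deletion and L858R, and also "T790M point mutation in methanesulfonate acid osimertinib tablets, ALK gene fusion and ROS1 gene fusion in crizotinib capsules".
- Section 4.1 sets the analysis unit: "For each gene locus, a four-grid table was used to calculate the positive coincidence rate", with the other agreement measures. It mentions no minimum count and no removal.
- Section 3.2.4 describes the blind: "The blind-editing file is kept independently by the blind-editing staff until the blind is solved". It does not mention decisions about which loci to keep.

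**The concern.** A rule that takes a locus out of the analysis has to say what is counted, what number is enough, who decides and when. This one says none of these. The 30% could apply to the whole sample set, to a gene or to a locus. The significance requirement has no test, alpha or precision. With several readings open and no link to the blind, the reading could be chosen once the counts, or the agreement results, are known.

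At stake is a stated purpose of the study. If T790M, ALK, ROS1 or either of the other two named EGFR alterations were left out, the study would give no result for a companion-diagnostic use it set out to assess, and Section 4.1's table for that locus would not appear. Leaving the locus out also discards information that a small number of positives does not harm: the negative coincidence rate and any samples positive on the panel only.

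**Working it through.** **The plan's own figure.** The total of 1,052 cannot be reproduced. The documents give no target coincidence rate, precision, alpha, power, prevalence or minimum number of positives from which it could follow. It is therefore no guide to what count per locus was intended.

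**Inputs.** N = 1,052 and the 30% ratio (Section 3.2.1); five companion-diagnostic alterations (Section 2); an EGFR mutation rate of up to 50% in Asian patients with advanced lung adenocarcinoma (Section 1); the Wilson interval with z = 1.96, which Section 4.1 uses when the rate exceeds 0.9. The documents give no frequency for T790M, ALK or ROS1.

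**Reading A: 30% at each locus.**

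- Positives needed: 0.30 × 1,052 = 315.6, so 316.
- Five companion-diagnostic loci: 5 × 316 = 1,580 positive calls from 1,052 samples. Since 1,052 / 316 = 3.3, at most three loci that do not overlap could qualify.
- Common EGFR alterations: assume the 50% rate holds in all samples and splits evenly between exon 19 deletion and L858R. Each then has 0.50 × 1,052 / 2 = 263 positives, and 263 / 1,052 = 25%, below 30%. Both would be left out.
- Less common alterations, at assumed prevalences of 1%, 5% and 10%: about 11, 53 and 105 positives expected, all far below 316.

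**Reading B: a significance test of association.** Take the smallest concordant table: A = 1, B = 0, C = 0, D = 1,051. Fisher's exact p = 1 / 1,052 = 0.00095. One concordant positive is enough, so almost nothing is left out.

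**Reading C: 30% across the study.** The ratio is then an enrolment target, and no locus has a number to meet. The removal sentence has nothing to act on except the undefined significance requirement.

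The same text thus supports leaving out all five companion-diagnostic alterations or virtually none.

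**What is lost if a sparse locus is left out.** With full agreement on n samples, the Wilson lower limit is n / (n + z²), with z² = 3.8416. Suppose, for illustration, 5 comparator-positives among 1,052:

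- Positive coincidence rate, 5/5: 5 / 8.8416 = 56.6%. This is weak.
- Negative coincidence rate, 1,047/1,047: 1,047 / 1,050.8416 = 99.6%. This is precise, and would be discarded.

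**What a defined minimum could look like.** By the same formula:

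- 22/22 gives 22 / 25.8416 = 85.1%, the smallest count to reach 85% (21/21 gives 84.5%).
- 35/35 gives 35 / 38.8416 = 90.1%, the smallest count to reach 90% (34/34 gives 89.8%).

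The 85% and 90% targets are illustrations and are not in the documents.

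**The case against.** The strongest reply has four parts.

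- **Wording.** The sentence may be permissive, or may mean only that no performance conclusion is drawn for a sparse locus. Section 4.1, the operative analysis text, covers each locus and contains no exclusion. This is possible, but the text does not settle it. Section 4.1 can equally be read as covering only the loci that remain.
- **Enrichment.** The samples are retrospective, and Section 6 says they were tested during earlier treatment. Section 3.2.2.1 also asks sites to "Collect some samples of relevant medical information before and after the use of targeted drugs", with prior molecular results. Positives can therefore be sought. This stands as a reason why removal may never arise, but no target per locus is set.
- **ROS1.** Section 3.3.2 asks sites to "add no less than 200 samples for ROS1 gene fusion detection kit", in addition to FISH. That figure counts samples, not positives. A reader might infer that a sparse PCR subset leaves ROS1 without a result; it does not, because the FISH comparison remains.
- **Prudence.** Withholding a claim when positives are few is sound. It is a reason to limit the claim, not to drop the data.

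A reader might also try to put a probability on removal. In unenriched sampling of 1,052, the chance of fewer than 10 positives is 96%, 39%, 0.3% and below 0.1% at assumed prevalences of 0.5%, 1%, 2% and 3%. These are not probabilities of removal: the plan contains no cut-off of 10, the prevalences are assumed, and the design permits enrichment.

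**Conclusion.** The point holds as a defect in the rule. Section 3.2.1 permits a companion-diagnostic locus to be left out against standards that cannot be applied as written, with no timing relative to unblinding and no exemption, contrary to the purpose in Section 2 and the analysis unit in Section 4.1. Its size is the spread between readings: from 316 positives per locus, which would exclude even exon 19 deletion and L858R at the assumed 25% each, to a single concordant positive.

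Two stronger conclusions are not supported. The documents do not show that any locus will be left out, and they do not allow the chance to be computed. Nor do they show that the risk is confined to T790M, ALK and ROS1: the two common EGFR alterations are safe only if the rule means enough positives, and not if it means 30% at each locus. The 25% figure rests on applying the Section 1 rate to all samples with an even split; the arithmetic of 316 and 1,580 needs no such assumption.

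**What to change.** 1. Delete the removal sentence from Section 3.2.1.
2. In Section 4.1, state that counts A to D and both coincidence rates, with Wilson intervals, are reported for every gene locus, including every alteration named in Section 2.
3. Before unblinding, fix a minimum number of comparator-positives for each companion-diagnostic locus, and justify it by the lower limit wanted for positive agreement. Counts of 22 and 35 correspond to 85% and 90% under full agreement; any disagreement requires more.
4. Below that minimum, keep the locus in the tables, label its positive coincidence rate descriptive, and make no positive-agreement claim for it.
5. State that the 30% is a study-wide enrolment target, or name its unit, and cross-refer Sections 3.2.1 and 4.1.

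The cost is protocol wording and some additional table rows; no new samples or assays are required. The downside is that wide intervals at rare loci become visible, and the claim for a sparse companion-diagnostic locus may have to be limited.

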#### 3.2.2 Inclusion Criteria, Exclusion Criteria Rejection Criteria of Study Subjects

#### 3.2.2.1 Inclusion Criteria

- (1) Clinically diagnosed as non-small cell lung cancer samples (mainly lung adenocarcinoma and some lung squamous cell carcinoma, adenosquamous carcinoma, large cell carcinoma, etc.), and a small number of other cancer types are enrolled as interference samples.
- (2) Collect some samples of relevant medical information before and after the use of targeted drugs.

  This part of the samples should have relevant previous molecular diagnosis results.

- (3) Able to provide samples in time according to the requirements of the plan: samples for DNA/RNA extraction: 10 pieces of 10 µm thickness for each sample or 10 pieces of paraffin rolls. Samples for FISH experiment: 5 slices of 3-4µm thickness.
- (4) The pathological examination conforms to the types of tissue samples listed in the above table. The HE staining results show that the tumor content is not less than 50%, and the paraffin slice damage should be avoided.
- (5) The sample should have corresponding basic clinical information, including: patient visiting number/medical record number/specimen number, age, gender, pathological diagnosis result, molecular diagnosis result (if any).

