#### 3.2.2.3 Rejection Criteria

- (1) Samples considered by the researcher to be unsuitable for continuing clinical trials, such as samples that have not been prepared in accordance with the required steps.
- (2) The amount of DNA and RNA extracted from the sample is insufficient, and the clinic can no longer provide more tissues for the extraction of DNA and RNA samples.
- (3) Samples whose results failed in repeated detections by the contrast method.
- (4) Sample patients with incomplete clinical basic information (visiting number/medical record number/specimen number, age, gender, pathological diagnosis results).
- (5) Samples that cannot be completed in a single test due to instrument or human factors (samples are contaminated during operation).

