#### 4.2 Kappa test

The Kappa test method was used to analyze the equivalence of clinical research reagents and comparison methods. Using statistical software, Kappa test was performed on the detection results of clinical research reagents and gold standard, and the k value was calculated. When k>0.75, clinical research reagents and comparison methods have good consistency.

$$Kappa = \frac{P_a - P_c}{1 - P_c}$$
, Where  $P_{a=} = \frac{A + D}{N}$ ,  $P_C = \frac{(A + B)(A + C)}{N} + \frac{(B + D)(C + D)}{N}$ 

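### T790M is judged on one table that mixes samples from before and after targeted drugs, so negative agreement, total agreement and kappa depend on a case mix the plan does not fix

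*Combined protocol and SAP*

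**What the plan says.** Section 2 lists the accuracy of the panel for "T790M point mutation in methanesulfonate acid osimertinib tablets" among its companion-diagnostic purposes, apart from exon 19 deletion and L858R.

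Section 3.2.2.1, criterion (2), reads "Collect some samples of relevant medical information before and after the use of targeted drugs" and asks that these samples have earlier molecular results. It gives no number or share for either group. Prior treatment is not among the basic clinical items in criterion (5). The matching rejection criterion in section 3.2.2.3 covers only "Sample patients with incomplete clinical basic information (visiting number/medical record number/specimen number, age, gender, pathological diagnosis results", so a sample with unknown treatment history stays in.

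Section 3.2.1 fixes only the overall size: "The total number of samples in this clinical trials is 1052". The planned positive share of at least 30% is not tied to T790M, and rare mutation types are to be counted as they occur clinically.

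Section 4.1 sets out the analysis: "For each gene locus, a four-grid table was used to calculate the positive coincidence rate, negative coincidence rate", then the predictive values and total agreement, with 95% intervals. Section 4.2 adds the only numerical agreement threshold in the plan: "When k>0.75, clinical research reagents and comparison methods have good consistency". No section divides a table by treatment status.

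**The concern.** The sampling plan treats exposure to targeted drugs as relevant, but the analysis does not use it. If T790M is seldom present without earlier EGFR-inhibitor treatment, most untreated samples land in cell D, negative by both methods. Such samples raise negative agreement and total agreement, and they can raise kappa, without saying anything about agreement in samples taken after treatment.

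At stake is the reading of the T790M result. The pooled kappa could meet the plan's threshold while kappa after treatment does not. A reader of the report could not tell, because the plan does not require the mix to be recorded or shown.

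**Working it through.** **Plan's own figure.** The documents give no T790M count, no T790M frequency before or after treatment and no split of the samples by treatment, so there is no planned T790M figure to reproduce. The total of 1052 is used below only as the pool size.

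**Inputs**
- Total samples: 1052 (section 3.2.1).
- Threshold: kappa above 0.75 (section 4.2).
- Rates (section 4.1): "Positive coincidence rate=A/(A+C)×100"%, negative agreement D/(B+D), positive predictive value (PPV) A/(A+B), total agreement (A+D)/N.
- Kappa = (Pa − Pc)/(1 − Pc), with Pa = (A+D)/N and Pc = [(A+B)(A+C) + (B+D)(C+D)]/N². The text shows division by N in Pc, possibly a fault of text extraction. The standard N² is used here.
- Assumed: 120 after-treatment samples with A=50, B=6, C=10, D=54.
- Assumed: the other 1052 − 120 = 932 samples are untreated and all negative by the comparison method.

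**Step 1: after-treatment samples alone**
- Positive agreement 50/60 = 83.3%; PPV 50/56 = 89.3%.
- Negative agreement 54/60 = 90.0%; total agreement 104/120 = 86.7%.
- Pa = 0.8667; Pc = (56×60 + 60×64)/120² = 7200/14400 = 0.500.
- Kappa = 0.3667/0.500 = **0.733**, below 0.75.

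**Step 2: add 932 double negatives (D = 54 + 932 = 986)**
- Positive agreement 50/60 = 83.3% and PPV 50/56 = 89.3%, both unchanged.
- Negative agreement 986/992 = 99.4%; total agreement 1036/1052 = 98.5%.
- Pa = 0.9848; Pc = (56×60 + 992×996)/1052² = 991392/1106704 = 0.8958.
- Kappa = 0.0890/0.1042 = **0.854**, above 0.75, with the same 16 errors.

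Fewer added samples suffice in this example. Ten double negatives (D=64) give 0.751, and 100 (D=154) give 0.813.

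**Step 3: vary the panel's false-positive rate f in the 932 added samples**

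B = 6 + 932f and D = 986 − 932f (expected counts). A and C do not change, so positive agreement stays at 83.3%.

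| f | B | D | Negative agreement | PPV | Kappa |
|---|---|---|---|---|---|
| 0% | 6 | 986 | 99.4% | 89.3% | 0.854 |
| 0.5% | 10.66 | 981.34 | 98.9% | 82.4% | 0.818 |
| 1% | 15.32 | 976.68 | 98.5% | 76.5% | 0.785 |
| 1.5% | 19.98 | 972.02 | 98.0% | 71.4% | 0.754 |
| 2% | 24.64 | 967.36 | 97.5% | 67.0% | 0.725 |
| 5% | 52.6 | 939.4 | 94.7% | 48.7% | 0.585 |

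Pooled kappa passes 0.75 with up to 14 false positives (14/932 = 1.5%). The gain over 0.733 is gone above about 1.8%, and beyond that pooling lowers kappa. Negative agreement is still above 90.0% in every row.

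**Step 4: other assumed after-treatment tables, pooled to 1052 with f = 0**
- 40/8/8/44: kappa goes from 0.679 to 0.825.
- 20/5/5/20: from 0.600 to 0.795.
- 30/10/10/50: from 0.583 to 0.740, still below the threshold.

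With A, B and C fixed, kappa cannot exceed 2A/(2A+B+C). For the main example that is 100/116 = 0.862.

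**The case against.** A reader might infer that pooling hides poor agreement after treatment altogether. The documents do not support that. Section 4.1 already requires positive agreement and PPV with intervals, and neither formula contains D. In the main example with f = 0, the 10 missed positives show in the 83.3% and the 6 false positives in the 89.3%, before and after pooling. This stands. It does not remove the point, because neither rate has a threshold, and the one criterion the plan states is the kappa that pooling can move.

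A reader might also infer that inflation is automatic, or that kappa mainly measures how many untreated samples were enrolled. Neither holds. Kappa has a ceiling set by the errors. One worse table fails even when pooled, and a false-positive rate of about 2% in the added samples removes the gain. The main example also starts only 0.017 below the threshold. The rarity of T790M without prior treatment, the 120/932 split and all cell counts are assumptions.

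Untreated samples are not useless either: they test for false-positive T790M calls. Section 2 does not restrict the T790M claim to treated patients. So the documents give no ground for resting the conclusion on after-treatment samples alone, nor for splitting exon 19 deletion and L858R in the same way.

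Finally, criterion (2) already seeks information around targeted-drug use. The larger gap is that the analysis never uses it.

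**Conclusion.** The point holds as a matter of what the pooled figures can and cannot show. The T790M negative agreement, total agreement and kappa depend on a mix of treated and untreated samples that the plan neither fixes nor requires to be reported. If T790M is rare without prior EGFR-inhibitor treatment, and the panel's false-positive rate in the added samples is low (at most about 1.5% in the main example), pooling can lift kappa from 0.733 to between 0.754 and 0.854. It then passes a threshold that the after-treatment samples fail. Negative agreement rises from 90.0% to between 98.0% and 99.4% over the same range.

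The size in the actual trial cannot be known from the documents. Other samples unlikely to carry T790M, such as the other cancer types enrolled as interference samples, act in the same way. This is an inexpensive improvement to a stated companion-diagnostic purpose. It does not show that the T790M conclusion will be wrong.

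**What to change.** - In section 3.2.2.1(5) and the case report form, add prior EGFR-inhibitor treatment at sampling: yes, no or unknown. The field should name EGFR inhibitors. Section 2 also covers crizotinib for ALK and ROS1, and samples taken after that drug would dilute a general after-treatment group.
- In sections 4.1 and 4.2, prespecify for T790M a separate 2×2 table for samples taken after EGFR-inhibitor treatment, with all agreement rates, their intervals and kappa. Report it beside the pooled table, with the number of samples in each treatment group, and state that it is considered in the T790M companion-diagnostic conclusion.
- Fix this before the codes are broken, so that the choice of table does not follow the results.

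**Cost.** One field, largely for information criterion (2) already seeks, and one extra table; no new assay or sample. Intervals in the after-treatment group will be wider. In the example, negative agreement of 90.0% on 60 samples has a 95% interval of 82.4% to 97.6% (0.900 ± 1.96×√(0.9×0.1/60), the plan's formula at p not above 0.9). The pooled 99.4% has 98.7% to 99.7% (Wilson). The T790M figure in that group will probably also look less favourable.
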